3.2 General Design - Neuroimaging Sub-Study

We propose to study a sub-sample of consecutively recruited participants (N=~50) enrolled in the parent randomized clinical trial. As displayed in **Figure 2**, an equal number of fMRI eligible smokers from the BAS+ or SC treatment group will be studied before treatment (~week -2) and during the final week of nicotine patch therapy (~week 7-8). As part of the parent study, smoking will be assessed by self-report and biochemically confirmed weekly after quitting, at EOT (week 8), and at the 12 and 26 week follow-ups. Weight will be assessed at these same time points. Food intake will be measured by three consecutive days of 24-hour food recalls at baseline and 4-, 8-, 12- and 26-weeks post-TQD.

Scans identified in **Figure 2** and included within the Study Procedures Section represent approximations. Participants will complete scans as designated in Figure 2 and the Study Procedures, but will be permitted a degree of flexibility at the discretion of the Principal Investigator due to extenuating circumstances.

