Smoking Cessation will be assessed and biochemically verified at EOT (week 8) and at 12-weeks post TQD as a primary outcome for the microbiome sub-study. A reliable and valid timeline follow-back method is used to assess daily smoking (presence and rate). The smoking outcome variable is 7-day point prevalence abstinence biochemically verified by CO < 5 ppm or Urine Cotinine assessment at a sensitivity of 100 ng/mL at EOT (week 8) and Follow-Up 1 and 2 visits (Week 12 and Week 26). Smoking status will also be biochemically confirmed by saliva cotinine < 15ng/ml at the 12- and 26-week follow-up.

Smoking Rate Timeline Follow Back (TLFB): A reliable and valid timeline follow-back method will be used to assess daily smoking (presence and rate) at every visit post Intake.

fMRI Tasks *Neuroimaging Sub-Study Only: See section 6.2.12: fMRI Scanning Visits for the complete descriptions of the in-scanner tasks.

Food Cue-Induced Craving. The key outcome for this variable is BOLD signal change for most appetizing foods (versus water, and versus least appetizing foods as an active control). Primary regions of interest for the BOLD fMRI analysis are insula, caudate, OFC and ACC. As a secondary measure, food craving will be assessed prior to and after completion of the scan. The food craving assessment is the 3-item "desire" subscale of the reliable and valid state version of the Food Craving Questionnaire (FCQ-S).

CONFIDENTIAL

This material is the property of the University of Pennsylvania. Do not disclose or use except as authorized in writing by the study sponsor

Relative Reinforcing Value of Food (via Food Reward Reinforcement/Choice task). The primary behavioral outcome will be the amount of additional effort subjects are willing to expend in order to obtain food. The primary regions of interest for the BOLD fMRI analysis are VS and vmPFC. Within these regions, the food choices (all 50 trials where food is an option) vs. fixation will be the primary contrast. Selection of this primary contrast will ensure the same stimuli will be analyzed across participants and conditions and maximize statistical power for detecting food-related activation.

Working Memory N-Back Task. Based on our prior work, the primary performance measure will be correct reaction time, and the secondary measure will be number correct; the primary regions of interest for the BOLD analysis will be DLPFC and medial/frontal cingulate gyrus.

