6.8 Sample Size Determination - Neuroimaging Sub-Study

We plan to test hypotheses at a global 5% Type I error (alpha) for each family of hypotheses, and have chosen a completed sample ($N=60$) that will achieve at least 80% power using 2-sided tests. Our analysis of power was based on “effect size” (standardized difference). Effect sizes were calculated from our own preliminary data, from published data summaries, and from published estimates of effects (e.g., t statistics, coefficients, p-values) using validated summary methods. We have several hypotheses and more than one outcome measure for some (e.g., different brain regions). We will control error in a family-wise manner, adjusting alpha (Bonferroni Aims 1 and 2, Hochberg step-up procedure for Aim 3) for the number of tests within each hypothesis family. Bonferroni corrections will also be adjusted for the correlations among multiple outcomes.

Aim 1 includes 2 hypotheses (**H1a&b**) regarding treatment effects on neural responses including 5 ROIs responding to food-related tasks. We test at $p<0.02$ because of the high correlation among ROIs within subjects ($\rho=0.54$). Estimates of effect size from our center data ($d=0.36$) indicate that we have 80% power to detect the effects. Aim 1 also tests hypothesis **H1c** for cessation effects. At the Bonferroni corrected threshold of $p=0.0167$, we have 80% power to detect small to medium effect sizes ($d=0.37$).

Aim 2 (H2a&b) essentially tests for mediation. The hypothesis that cessation increases food intake will be tested at 0.05, with power for effect sizes $\sim d=0.32$ [9, 58]. For Aim 2b (ROIs predicting food intake), we expect a weaker correlation than H1a ($\rho=0.4$), and our adjusted threshold for significance is $p<0.01$. Expected effect sizes are approximately 0.5, and we expect 96% power to detect the effects.

Aim 3 begins with the model in Aim 2b above, and tests interacting effects of working memory-related BOLD signal and food reinforcement (or food cue reactivity) on food intake. We will reduce the complexity of this analysis by using difference scores (pre minus post) to model a 2-

CONFIDENTIAL

This material is the property of the University of Pennsylvania. Do not disclose or use except as authorized in writing by the study sponsor

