6.11 Statistical Methods - Neuroimaging Sub-Study

fMRI preprocessing will use standard algorithms in FSL (FMRIB's Software Library, www.fmrib.ox.ac.uk/fsl) including distortion correction, slice-time correction, motion correction, spatial smoothing, high-pass filtering (120s) and co-registration to the structural MRI. Quality assessment (QA) procedures will examine global and ROI based temporal signal-to-noise ratio (tSNR), absolute and relative motion, and signal spike count. Following preprocessing, subject-level BOLD timeseries analysis is carried out using the general linear model (GLM) as implemented in FSL, with a canonical double-gamma hemodynamic response function (HRF) for convolution, and linear contrasts to estimate task-specific BOLD responses for each individual session. To enhance sensitivity and reliability, including motion regressors in the model will reduce potential motion artifact. For group-level Image analysis, Subject-level statistical maps will be transformed into a common anatomic space (Montreal Neurological Institute, MNI) for group-level analysis. A priori region of interest (ROI) analyses will focus on specific regions for each task. For the n-back, primary ROIs will be MF/CG, and bilateral DLPFC. For the cue and reinforcement tasks, primary ROIs will be VS and ventromedial PFC; secondary ROIs will include MF/CG, amygdala, OFC, and insula. Percent signal change and activation extent within these ROIs will be used for statistical tests of key hypotheses. In addition, we will use voxel-wise random effects analysis in FSL to test for the effects outside of predicted regions. These voxelwise analyses will be conservatively corrected using $Z>3.09$ and cluster probability (family-wise error) $p<0.001$.

Hypothesis Testing. Percent signal change data will be exported for hypothesis testing using Stata (StataCorp, Texas).

CONFIDENTIAL

This material is the property of the University of Pennsylvania. Do not disclose or use except as authorized in writing by the study sponsor

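### Neuroimaging Aim 1 sets its p<0.02 threshold by counting 5 regions, but the plan describes 6 to 10 tests on percent signal change, and more if activation extent is also tested

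*Combined protocol and SAP*

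**What the plan says.** Section 6.8 opens with the commitment "We plan to test hypotheses at a global 5% Type I error (alpha) for each family of hypotheses" and says that alpha will be adjusted for the number of tests in each family, with Bonferroni for Aims 1 and 2 relaxed for correlation among outcomes. For Aim 1 it describes two hypotheses "regarding treatment effects on neural responses including 5 ROIs responding to food-related tasks" and gives p<0.02 as the threshold "because of the high correlation among ROIs within subjects", with a correlation of 0.54. This is the only threshold printed for H1a and H1b.

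The tests themselves are described elsewhere:

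- **Section 2.2.** H1a (cue task) names insula, ACC, OFC and VS/NAC. H1b (choice task) names VS/NAC and vmPFC.
- **Section 6.5.6.** The key outcome of the cue task is "BOLD signal change for most appetizing foods (versus water, and versus least appetizing foods as an active control". For the choice task, by contrast, one primary contrast is named (food choices versus fixation).
- **Section 6.11.** "Percent signal change and activation extent within these ROIs will be used for statistical tests of key hypotheses". The paragraph headed Hypothesis Testing then exports only percent signal change to Stata. This section also lists just two primary ROIs, VS and vmPFC, for the cue and choice tasks.

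**The concern.** The threshold was set by counting brain regions, but error accumulates over tests. VS/NAC is tested in both tasks, the cue task has two contrasts, and one sentence adds a second BOLD measure. No section says which cue contrast decides H1a, and section 6.11 is inconsistent on the measure.

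A BAS+ effect on brain response could therefore be claimed from whichever contrast (or measure) falls below 0.02, at more than the promised 5% error. Two contrasts could also disagree with no rule for which one governs. The ambiguity carries forward, because section 6.8 restricts Aim 3 to the ROIs found sensitive to treatment in Aim 1.

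**Working it through.** **Inputs from the documents:** family-wise alpha 0.05, two-sided tests, 5 ROIs, threshold 0.02 and correlation 0.54 between ROIs (6.8); regions by task (2.2); contrasts (6.5.6); measures and the shorter ROI list (6.11). Correlations between contrasts and between measures are not given, so they are assumptions below.

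**1. The plan's own figure.** No formula is named. A common correlation-adjusted Bonferroni is α/m^(1−ρ). With m=5 and ρ=0.54 it gives 0.05/5^0.46 = 0.05/2.097 = 0.0238, which rounds to the printed 0.02. The same formula gives 0.05/5^0.5 = 0.0224 for Aim 3 (5 tests, correlation 0.5), also printed as 0.02. This is very likely how 0.02 arose.

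**2. Counting tests.**

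| Reading | Count |
|---|---|
| Regions of 2.2, one measure, one cue contrast | 4 + 2 = 6 |
| Regions of 2.2, percent signal change, both cue contrasts | 4×2 + 2 = 10 |
| Regions of 2.2, both measures, both cue contrasts | 10×2 = 20 |
| Two primary ROIs of 6.11, percent signal change, both cue contrasts | 2×2 + 2 = 6 |
| Two primary ROIs of 6.11, both measures, both cue contrasts | 6×2 = 12 |

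**3. Family-wise error.** For m two-sided z-tests with common correlation ρ and c = Φ⁻¹(1−α/2):

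FWER = 1 − ∫ [Φ((c−√ρ·u)/√(1−ρ)) − Φ((−c−√ρ·u)/√(1−ρ))]^m φ(u) du

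With ρ=0.54 for every pair of tests (documented between ROIs only):

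| Tests | At 0.02 | At 0.0125 |
|---|---|---|
| 5 | 7.8% | 5.0% |
| 6 | 8.9% | 5.8% |
| 10 | 12.7% | 8.4% |
| 12 | 14.3% | 9.6% |
| 20 | 19.6% | 13.4% |

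The right-hand column starts from a threshold that holds 5% for 5 tests at this correlation, so it isolates what the uncounted tests add. The middle column also contains the excess already present with 5 tests at 0.02.

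**4. Sensitivity to the correlation, at 0.02.** For common correlations of 0.7 to 0.3, 6 tests give 7.3% to 10.6%, 10 give 9.9% to 16.2%, and 20 give 14% to 27%. A structured version kept 0.54 between ROIs and assumed 0.5 to 0.9 between measures and between contrasts and 0.3 to 0.9 between tasks. It gave about 11% to 15% for 10 tests and 15% to 26% for 20.

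**5. Threshold that holds 5% at ρ=0.54.** For 6 tests it is 0.0106 (plain Bonferroni 0.05/6 = 0.0083). For 10 tests it is 0.0069 (plain Bonferroni 0.0050).

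**The case against.** The strongest reply is that section 6.8 already contains the governing rule: alpha is adjusted for the number of tests in the family. On that view 0.02 is a planning figure that would be rescaled when the tests are run. This has some force, but 0.02 is stated as the level at which H1a and H1b are tested, section 6.11 gives no other, and the rule cannot be applied until the tests are fixed.

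Second, by the formula the plan appears to use, 6 tests give 0.0219, which still prints as 0.02. That is correct, so the move from 5 to 6 alone does not disturb the printed figure. Ten tests give 0.0173 and 20 give 0.0126, both below 0.02.

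Third, a reader might infer from the activation-extent sentence that the plan commits to 20 tests. The documents do not support that as the main reading. The Hypothesis Testing paragraph exports percent signal change only, section 6.5.6 defines the cue outcome as BOLD signal change, and activation extent appears nowhere else and has no model of its own.

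Fourth, a reader might infer that the excess is the same whichever ROI list applies. It is not: the two primary ROIs of 6.11 with percent signal change give only 6 tests.

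Finally, section 1.2 calls BOLD signal a secondary outcome and Aim 1 concerns putative mechanisms. The plan speaks of key hypotheses and does not label these tests confirmatory. That limits what is at stake, but the 5% commitment is the plan's own. The cue contrasts are also partly ranked, since the least-appetizing comparison is called an active control, but neither is named primary.

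**Conclusion.** The point holds in a limited form. The printed threshold counts 5 regions, while the plan describes 6 to 10 tests on percent signal change, and at most 20 if activation extent is tested too. At p<0.02 the family-wise rate is about 8.9% for 6 tests and 12.7% for 10, with 19.6% as the upper case, against a stated 5%. Of this, 7.8% is already present with 5 tests. The uncounted tests by themselves take a correctly set 5% to about 5.8%, 8.4% and 13.4%.

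These rates assume that every test uses the same threshold, that the global null holds, and that one correlation of 0.54 applies throughout. Only the between-ROI value is documented, and the ranges above show the dependence. The error control of the parent trial's weight and abstinence outcomes is not affected.

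**What to change.** - **Section 6.11:** make percent signal change the only measure for the key hypothesis tests, and call activation extent descriptive.
- **Section 6.5.6:** name one primary cue contrast, for example most appetizing versus water, with the other contrast supportive.
- **Section 6.8:** use one ROI list throughout and restate the threshold for the resulting region-by-task tests. With the regions of 2.2 this is 6 tests: about 0.0106 at correlation 0.54, or 0.0083 by plain Bonferroni if no correlation is to be assumed. Name the formula used, and restate the power at the new threshold.

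This is a change of wording, to be made before unmasked analysis, and needs no new data. Activation extent and the second cue contrast become supportive, and the power statement becomes slightly less favourable. For scale only, a one-sample z formula with the N=60 of 6.8, (z₁₋α/₂ + 0.842)/√60, puts the smallest effect detectable with 80% power at 0.409 for α=0.02 (z=2.326) and 0.439 for α=0.0106 (z=2.556). The actual figure depends on the between-arm mixed model, whose inputs the documents do not give.

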This neuroimaging study will aim to examine a sub-set of the randomized clinical trial participants. Functional magnetic resonance imaging (fMRI) can identify mechanisms underlying behavior change beyond self-report and behavioral measures. We will examine neural responses in three parallel pathways including: cognitive control, food cue reactivity, and food reinforcement. As in the parent study, the primary outcomes will be food intake and 7-day point prevalence abstinence at 12 weeks post target quit date. BOLD signal (secondary outcome) will be measured at pre-treatment (week -2) and end of treatment (week 8). Our three aims address: 1) identifying putative brain mechanisms underlying BAS+ (vs. SC) treatment for smoking cessation and PCWG; 2) evaluating the relative contribution of treatment-induced changes in task related brain signal (Food Cue Response, Food Reinforcement/Choice) in prediction of post treatment food intake; and 3) testing whether BAS+ (vs. SC) induced change in neural responses to food cues and food reinforcement is a stronger predictor of food intake among smokers with greater cognitive control. The findings will address *why* BAS+ may be effective in managing PCWG and provide insight into which patients are best supported by this treatment. We also test whether cognitive control processes moderate the influence of BAS+ treatment on food intake.

1.3 *Background- Microbiome Sub-Study*

The Gut Microbiome May Underpin the Substitution of Food for Cigarettes After Smoking Cessation: Converging research suggests that the gut microbiome may play an important role in modulating post-cessation increases in food intake and set the stage for smoking relapse. Gut bacteria and the brain have a bi-directional route of communication through the microbiome-gut-brain (MGB) axis. As such, smoking cessation-induced perturbations in the gut microbiome have the potential to impact the brain as well as behavior. Preliminary research has shown that smoking cessation results in profound changes in gut microbial abundance within 4

CONFIDENTIAL

This material is the property of the University of Pennsylvania. Do not disclose or use except as authorized in writing by the study sponsor

to 8 weeks after quitting smoking (see Aim 1). These smoking cessation-associated changes (e.g., reduced *Bacteroides*, increased *Firmicutes*) are similar to those observed in obesity.

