2.2 Neuroimaging Sub-Study

Aim 1: Identify putative brain mechanisms underlying BAS+ (vs. SC) treatment for smoking cessation and PCWG.

H1a: BAS+ (vs. SC) will decrease food cue-induced activity in insula, anterior cingulate cortex (ACC), orbitofrontal cortex (OFC), and ventral striatum/accumbens (VS/NAC);

H1b and H1c: (Hb) BAS+ (vs. SC) will decrease food reinforcement choice-related activity in VS/NAC and ventromedial prefrontal cortex (vmPFC); and **(H1c)** will produce corresponding decreases in food craving, reward, and reinforcement at the behavioral level (task performance).

Aim 2: To evaluate the relative contribution of treatment-induced changes in task related brain signal (Food Cue Response, Food Reinforcement/Choice) in prediction of post treatment food intake.

H2a: Brain network response (H1a-b) in the BAS+ (vs. SC) group will characterize treatment-induced changes in caloric intake (and quit success) more accurately than clinical (age, sex, nicotine dependence, BMI) and behavioral (withdrawal, craving, food reinforcement) measures alone.

H2b: The relative contribution of domain specific brain signal (food cue reactivity and food reward) to the prediction of treatment-induced change in caloric intake will be evaluated (regression model).

Aim 3: Test whether BAS+ (vs. SC) induced change in neural responses to food cues and food reinforcement is a stronger predictor of food intake among smokers with greater cognitive control.

We predict that the relationship of food cue and choice-related neural activity (e.g., VS/NAC BOLD signal; BAS+ vs. SC) will be a stronger predictor of caloric intake among smokers who also show greater working memory-related neural activity (i.e., DLPFC BOLD signal) at baseline and post treatment. Regions of interest for food cue and choice-related neural activity will be selected from those shown to be sensitive to cessation in Aim 1.

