Aim 1: Identify effects of BAS+ (vs SC) treatment on food related neural activity and behavior: These comparisons are all between subject, and will be analyzed using mixed models regression (xtmixed, StataCorp, Texas). The model predictors will include a binary indicator for group (BAS+ vs. SC). The hypothesis will be tested using the z-score corresponding to the main effect of group. Covariates can be included in the model to control error (sex, BMI, nicotine dependence, age, weight concerns), although we do not expect to make large gains for adding subject-level controlling variables in a mixed model.

Aim 2: Evaluate the relative contribution of these neural processes to post-cessation caloric intake: Our outcome variable is average daily calories based on food recalls. The first comparison (pre vs. post-treatment) is within-subject, and will be analyzed using mixed models regression with subject specific random effects. As before, we include a binary predictor for condition, a categorical indicator for serial day, and we will test using the z-score corresponding to condition. For testing candidate mediators, we will again model calories using mixed models, entering variables as time-varying (condition varying) predictors, along with subject specific random effects. Finally, we will build the larger model, looking for confounding that represents potential mediation. For this purpose, we will use regression-based multi-equation path models. Path Analysis partitions a directly measured bivariate relationship, for example, between abstinence and calories ingested, into direct and indirect causal paths, to tease apart the important components mediating the response. We will deem that mediation has occurred when a relationship between abstinence and food intake accounted in full, or in part, by one or more of the intervening variables (BOLD signal change or subjective responses in cessation vs. smoking). We will assess the strength of the indirect effects through confidence intervals, evaluate the proportion mediated (i.e., partial or complete mediation), and determine significance with Delta method standard errors. To assess the level of mediation for a pathway, we will estimate the ratio of the indirect effect to the total effect (i.e., effect proportion mediated $\beta_{\text{indirect}}/\beta_{\text{total}}$).

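### Neuroimaging Aim 1 is tested by the main effect of group without saying what the outcome is or how the pre-treatment scan enters; the readings left open lose power, and the test should be Scan 2 adjusted for Scan 1

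*Combined protocol and SAP*

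**What the plan says.** Section 2.2 states the hypotheses as decreases. H1a reads: "BAS+ (vs. SC) will decrease food cue-induced activity in insula, anterior cingulate cortex (ACC), orbitofrontal cortex (OFC), and ventral striatum/accumbens (VS/NAC". H1b says the same of choice-related activity, and H1c of craving, reward and reinforcement in behaviour.

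Section 1.2 gives two measurement times: "BOLD signal (secondary outcome) will be measured at pre-treatment (week -2) and end of treatment (week 8". Section 6.2.13 places Scan 1 before the Baseline Visit, and section 6.2.3 places the first counselling session at that visit. Scan 1 is therefore a true pre-treatment measurement.

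The Aim 1 paragraph of section 6.11 sets out the analysis:

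- Type of comparison: "These comparisons are all between subject, and will be analyzed using mixed models regression (xtmixed, StataCorp, Texas".
- Predictors: "The model predictors will include a binary indicator for group (BAS+ vs. SC".
- Test: "The hypothesis will be tested using the z-score corresponding to the main effect of group".
- Covariates: "Covariates can be included in the model to control error (sex, BMI, nicotine dependence, age, weight concerns". The paragraph adds "although we do not expect to make large gains for adding subject-level controlling variables in a mixed model".

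It names no scan or time term, no group-by-scan term, no Scan 1 covariate and no change-score outcome. Pre/post difference scores are specified only for Aim 3 (sections 6.8 and 6.11).

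**The concern.** A hypothesis about a treatment-induced decrease, measured by one scan before treatment and one at its end, needs a test that says how the two scans are combined. A bare main effect of group does not. If both scans are rows in the mixed model, the main effect averages a pre-treatment difference whose expectation is zero with the post-treatment difference that matters. If only Scan 2 is analysed, a costly baseline measurement goes unused.

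What is at stake is the chance of detecting a real effect in a sample of about 50 to 60. The consequence does not stop at Aim 1: sections 2.2 and 6.8 restrict Aim 3 to regions that Aim 1 finds sensitive to treatment, so a region missed in Aim 1 is never tested there.

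**Working it through.** **Inputs from the plan.** Two scans and equal arms (section 3.2). Section 6.8 gives completed N = 60, two-sided tests, alpha 0.02 for H1a and H1b, d = 0.36 and a stated power of 80%. The correlation of 0.54 in section 6.8 is between regions, not between scans.

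**Assumed.** The correlation r between Scan 1 and Scan 2 is not in the documents; I use 0.3, 0.5 and 0.7. Unit SD at each scan. Expected group difference zero at Scan 1 and d at Scan 2.

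**The plan's own figure first.** For a two-group comparison with 30 per arm, the non-centrality is 0.36 / sqrt(2/30) = 1.394. Power = Phi(1.394 − 2.326) = 17.6%, not 80%. Reaching 80% would take 2 × ((2.326 + 0.842)/0.36)² ≈ 155 per arm. A one-sample calculation needs ((2.326 + 0.842)/0.36)² ≈ 77 people, so the stated 80% is close to a within-subject test in about 77 people and does not describe the between-group test in section 6.11.

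**Expected estimate and SD for each way of using the scans.**

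| Analysis | Estimates | SD per subject |
|---|---|---|
| Main effect over both scans | d/2 | sqrt((1+r)/2) |
| Scan 2 only | d | 1 |
| Change score (or group × scan) | d | sqrt(2(1−r)) |
| Scan 2 adjusted for Scan 1 | d | sqrt(1−r²) |

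**Relative efficiency.** Divide each non-centrality by that of the adjusted test:

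- main effect: 0.5 × sqrt(1−r²) / sqrt((1+r)/2) = 0.59 / 0.50 / 0.39 at r = 0.3 / 0.5 / 0.7
- Scan 2 only: sqrt(1−r²) = 0.95 / 0.87 / 0.71
- change score: sqrt(1−r²) / sqrt(2(1−r)) = 0.81 / 0.87 / 0.92

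**Power where the adjusted test has 80%, alpha 0.05.** Power = Phi(ratio × 2.802 − 1.960). For example, the main effect at r = 0.5: Phi(0.50 × 2.802 − 1.960) = 29%.

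| Analysis | r = 0.3 | r = 0.5 | r = 0.7 |
|---|---|---|---|
| Main effect over both scans | 38% | 29% | 19% |
| Scan 2 only | 76% | 68% | 52% |
| Change score | 62% | 68% | 73% |

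At alpha 0.02 the two-scan main effect has 33% / 23% / 14%. For equal power it needs 1/ratio² = 2.9 / 4.0 / 6.7 times the sample of the adjusted test.

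**Simulation check.** With d = 0.82, r = 0.5, 30 per arm, alpha 0.02 and 20,000 runs, the two-scan main effect averaged 0.41, half the true difference, with 30% power. Scan 2 only had 79% and the change score 78%.

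**At the plan's effect size** (d = 0.36, N = 60, alpha 0.02, r = 0.3 / 0.5 / 0.7): two-scan main effect 7.2% / 6.4% / 5.8%; Scan 2 only 17.6%; change score 12.5% / 17.6% / 29.9%; Scan 2 adjusted for Scan 1 19.4% / 23.7% / 35.4%.

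**The case against.** The strongest reply is that the paragraph leaves the outcome unstated and need not be wrong. The predictor list may not be exhaustive. The outcome could be the pre/post change with regions as the repeated measure: section 6.8 gives five regions correlated within subject, which would explain a mixed model for comparisons called between-subject, and Aims 2 and 3 speak of change. On that reading the group main effect does test change. This stands as a possibility, and it is why the half-effect result must stay conditional. But section 6.11 says none of it for Aim 1. Responses there are estimated for each session, and the exported percent signal change is a within-session task contrast. A change score would in any case be less efficient than adjustment. Nor would adding a group-by-scan term rescue the named test: with Scan 1 as the reference level, the group coefficient would be the pre-treatment difference.

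A reader might infer that the planned test cannot address H1a to H1c, or that a true reduction would usually be missed. The documents do not support either as a general statement. A randomised comparison of Scan 2 alone is a valid test of whether BAS+ lowers activity, and only the two-scan reading falls to 19-38%. A reader might also infer that chance imbalance at Scan 1 produces false positives. It does not: such imbalance enters the estimate only if the scans are pooled, and there it is part of the standard error, so type I error is held.

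It is also fair that the remark about covariates is not shown to be wrong. How much sex, BMI or dependence explain of the BOLD signal is an empirical matter, and no document gives a figure. The remark is unsupported, no more.

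**Conclusion.** The concern holds as a specification gap with a measurable cost. Section 6.11 names a tested term but neither the outcome nor the role of Scan 1, and every way of filling the gap considered here is less powerful than Scan 2 adjusted for Scan 1. The loss is largest if both scans are pooled, moderate if only Scan 2 or a change score is used. These sizes rest on an assumed scan-to-scan correlation of 0.3 to 0.7, equal variances, and no expected group difference before treatment.

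The better test does not bring Aim 1 to its stated 80% power at d = 0.36, so the power statement in section 6.8 needs correcting as well. The matter is a should-fix: BOLD signal is a secondary outcome of a mechanistic sub-study, and the parent trial's weight and abstinence outcomes are untouched.

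**What to change.** In section 6.11, Aim 1, replace the sentence naming the test with wording such as: *For each region of interest and behavioural measure, the hypothesis is tested by the BAS+ vs SC coefficient for the Scan 2 value, adjusted for the Scan 1 value of the same measure and for the randomisation factors gender, BMI and nicotine dependence.* A mixed model with both scans, the group means constrained to be equal at Scan 1 and the group-by-scan term tested, would serve equally well. The adjustment factors are those used for stratification in section 3.1.

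In section 6.8, restate the Aim 1 power for this between-group test, giving the assumed scan-to-scan correlation and the completed sample. That section uses 60, while sections 3.2 and 4.3 plan for about 50.

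Deleting the remark on small covariate gains is optional. The cost is a change of wording and a fresh power calculation; both scans are already in the schedule.
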